5.3 Lifestyle Considerations

Not applicable.

5.4 Screen Failures

Screen failures are defined as participants who consent to participate in the clinical trial but are not subsequently randomly assigned to the study intervention or entered in the study. A minimal set of screen failure information is required to ensure transparent reporting of screen failure participants, to meet the Consolidated Standards of Reporting Trials (CONSORT) publishing requirements and to respond to queries from regulatory authorities. Minimal information includes demography, screen failure details, eligibility criteria, and any serious adverse event (SAE).

5.5 Strategies for Recruitment and Retention

Patients presenting to the EDs of HUP, PPMC, PAH, or HUP Cedar with knee pain for whom plain film imaging has been obtained will be screened by a member of study team to determine eligibility based on inclusion and exclusion criteria described in sections 5.1 and 5.2. If the patient is eligible, a member of study team will approach the patient to obtain informed consent.

- Target sample size: 17 patients in both the intervention and control treatment arms
- Anticipated accrual rate: 100%
- Anticipated number of sites and in which participants are to be enrolled: 4 clinical sites (EDs of HUP, PPMC, PAH, or HUP Cedar)
- Source of participants: ED patients
- Recruitment venues: ED
- How potential participants will be identified and approached: (1) Potentially eligible patients under the care of a participating physician will be identified and approached

during the usual course of care. (2) Potentially eligible patients who are not under the direct care of a participating physician will be identified by chart screening and direct communication with the primary physician by either participating physicians or research assistants.

6 STUDY INTERVENTION

6.1 Study Intervention(s) Administration

6.1.1 *Study Intervention Description*

The study interventions are either conventional analgesia or a one-time three-point GNB with weight-based 0.5% bupivacaine and 4 mL dexamethasone divided into three separate injections, ~~around the SMGN, SLGN, and IMGN. Bupivacaine and dexamethasone are commercially~~ available and are being used in accordance with approved labeling.

For participants randomized to the GNB arm, pre-procedural ultrasound will be performed to evaluate the target sites of injection (e.g., superomedial femoral condyle, the superolateral femoral condyle, and the inferomedial fibular condyle) on the superomedial, superolateral, and inferomedial aspects of the knee. Color doppler will be used to identify any of the geniculate arteries (superomedial, superolateral, and inferomedial geniculate arteries) which may be present in proximity to their respective genicular nerves. Once the target signs have been obtained; the entire knee will be prepped with chlorhexidine antiseptic and draped in standard fashion. Using sterile conditions (including single sterile gloves), a 5-15 MHz linear ultrasound transducer will be prepared with a sterile ultrasound probe cover and sterile ultrasound gel. The ultrasound will be placed in a cephalad to caudad direction with the probe indicator facing cephalad, and color doppler will be always on during the procedure for real time visualization of potential vasculature. For each injection, a separate needle will be used to minimize the risk of infection. In most cases, we will use 1.5-inch 20 or 22-gauge hypodermic needles, however for patients with larger body habitus requiring more depth and a longer needle, a 20- or 22-gauge 3.5-inch Quincke spinal needle will be used. For the superomedial and superolateral blocks, the needle will be introduced from a cephalad to caudad direction (toward the knee) and for the inferomedial block, the needle will be advanced from a caudad to cephalad direction (toward the knee). In all cases, the needle will be advanced toward the periosteum under constant visualization, taking care to avoid any potential vascular structures. Once the needle contacts the periosteum, aspiration will be performed to ensure the needle tip is not within a vascular structure, at which time a small aliquot of anesthetic will be injected to lift the muscle off the periosteum and periosteal fat pad. Once proper lifting has been visualized, the remainder of anesthetic will be slowly administered over the span of 30-seconds while maintaining sonographic visualization of the needle tip. Upon deposition of anesthetic at each site, the needle will be removed, and the site of skin puncture will be covered with a taped piece of gauze or bandage.

Participants randomized to conventional analgesia, will be treated with standard medication(s) which include any oral, topical, or intravenous analgesic, including but not limited to acetaminophen, non-steroidal anti-inflammatory drugs (NSAIDs), lidocaine patches, opioids. These are all commercially available, many of which available over the counter, and are being used in accordance with approved labeling.

No experimental agents are being used in this study. No experimental off label devices are being used in this study.

6.1.2 *Dosing and Administration*

For the GNB arm, dosing is determined based on ideal body weight such that the total amount of bupivacaine will fall well under the maximum recommended dosing by weight (2.5 mg/kg ideal body weight). In this case, 80% of ideal body weight-based (actual body weight for patients with BMI less than 25 kg/m²) dosing of 0.5% bupivacaine (as previously described) and 4 mg dexamethasone, divided into three injections around the affected knee, one each around the SMGN, SLGN, and IMGN. Administration of each injection will occur over the span of one minute to monitor for potential adverse effects to ensure the maximal degree of safety. If any signs or symptoms of LAST occur (e.g., tachy- or brady-dysrhythmias, hyper- or hypotension), or if a patient reports subjective feelings of dizziness, confusion, or tingling (including perioral or tongue paresthesia), the injection will be halted immediately. Participants will be instructed to immediately alert the physician if any of these symptoms occur.

There is a precaution issued by the FDA regarding use of bupivacaine in geriatric patients specifically stating that "Clinical studies of bupivacaine did not include sufficient numbers of subjects aged 65 and over to determine whether they respond differently from younger subjects. In general, dose selection for an elderly patient should be cautious, usually starting at the low end of the dosing range." While this is not contraindicated in geriatric patients, caution is recommended as elderly patients may have age-related physiological changes that can affect the pharmacokinetics and pharmacodynamics of bupivacaine including decreased metabolism and reduced plasma protein binding. Therefore, it is recommended to utilize dosing at less than maximally recommended doses and monitor closely for adverse effects. To minimize these risks, we are utilizing 80% of their ideal body weight dosing of bupivacaine. Furthermore, all patients will be monitored in the ED for at least 30 minutes after the block. Should an adverse event occur, reversal therapy will immediately be available (see Section 6.5 for details).

The GNB will be performed under clean conditions (e.g., sterile gloves, chlorhexidine skin prep that will be allowed to completely dry before puncturing the skin) and under ultrasound guidance.

For the control arm, conventional anesthetics will be dosed at the discretion of the primary provider caring for the patient and will include standard dosing of medications. This includes but is not limited to: 1) oral acetaminophen 325 mg to 975 mg, 2) oral ibuprofen 400 mg to 600 mg, 3) intravenous ketorolac 15 mg to 30 mg, 4) topical 5% lidocaine patches, 5) oral oxycodone 5 mg to 20 mg, 6) intravenous morphine 0.05 mg/kg to 0.1 mg/kg, or 7) intravenous hydromorphone 0.015 mg/kg to 0.03 mg/kg.

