1 STUDY SUMMARY

1.1 Synopsis

Title: Ultrasound-Guided Genicular Nerve Block for Knee Pain in the Emergency Department: A Randomized Controlled Trial

Short Title: Genicular Block for Knee Pain: An RCT

Study Description: Patients who present to the emergency department (ED) at any of the clinical sites of the University of Pennsylvania Health System with atraumatic knee pain will be considered for enrollment to be randomized to receive an ultrasound-guided genicular nerve block (GNB) or conventional analgesia. Patients randomized to the intervention arm will receive a three-point GNB with weight-based dosing 0.5% bupivacaine augmented with 4 mg dexamethasone, divided into three separate aliquots to be injected around the superomedial genicular nerve (SMGN), superolateral genicular nerve (SLGN), and inferomedial genicular nerve (IMGN). This will be an open-labeled, investigator-initiated study with convenience enrollment.

Objectives: Primary Objective:

- To determine whether patients receiving a GNB for knee pain experience greater pain reduction compared to conventional analgesia

Secondary Objectives:

- To determine whether patients who receive a GNB experience a longer duration of analgesia compared to those who receive conventional analgesia
- To determine whether patients who receive a GNB report higher patient satisfaction compared to those who receive conventional analgesia
- To determine whether patients who receive a GNB have shorter ED length of stay (LOS) compared to those who receive conventional analgesia

Primary Endpoint:

- Difference in pain level as measured by NRS at pre-intervention (GNB or conventional analgesia) and at either 1-hour post-enrollment or time of ED discharge, whichever occurs first

Secondary Endpoints:	
• Difference in duration of analgesia, assessed at 24-36 hours post intervention.• Difference in APS-POQ-RED between treatment arms, assessed at either 1-hour post-enrollment or time of ED discharge, whichever occurs first.• Difference in ED LOS between treatment arms, as determined by time from enrollment in study to time of ED discharge.

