Study Population:	
Patients presenting with knee pain at any of the four emergency departments: (1) Hospital of the University of Pennsylvania (HUP), (2) Penn Presbyterian Medical Center (PPMC), (3) Pennsylvania Hospital (PAH), and (4) HUP Cedar (Cedar)
 
All genders, age \geq 18, all demographic groups
 
Moderate to severe knee pain (pain measured on NRS between 5 and 10)
 
Exclusions based on general health status: cognitive impairment / dementia, inability to consent for study procedure
 
Exclusion criteria: pregnant; incarcerated; large knee joint effusion as identified on plain film radiography; acute traumatic etiology for knee pain including fracture, dislocation, or suspected tendonous or ligamentous injury; concern for infection including septic joint, abscess, cellulitis, or sepsis; hemodynamic instability; allergy or contraindication to bupivacaine or any of its components
 
Sample size: 17 patients per treatment arm

Phase:	N/A
Description of Sites/Facilities	
(1) Hospital of the University of Pennsylvania
 
(2) Penn Presbyterian Medical Center
 
(3) Pennsylvania Hospital
 
(4) HUP Cedar

Enrolling Sites:	EDs of the four previously mentioned sites
Description of Study Intervention:	The study intervention is an ultrasound-guided three-point GNB, which involves injection of local anesthetic with adjuvant (ideal bodyweight-dosed bupivacaine 0.5% and dexamethasone 4 mg) around the genicular nerves of the knee. The genicular nerves are a series of four terminal

sensory nerve branches of the femoral nerve that provide sensory innervation to the joint capsule of the knee, thereby providing pain relief without motor blockade or paralysis. See detailed description of the study intervention in Section 6. The comparison control arm involves conventional analgesia for knee pain, which includes oral, intravenous, or topical analgesics (e.g., acetaminophen, non-steroidal anti-inflammatory drugs [NSAIDs], opioids, lidocaine patches, heating or cold packs) and will be determined at the discretion of the primary provider caring for the patient. See detailed description of study control arm in Section 6.

Study Duration: 12-months

[figure not shown]
Participant Duration: 24 to 36-hours

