Those patients who satisfy all inclusion criteria will be offered enrollment and consented by a participating emergency physician or RA. Upon consenting, patients will be asked to rate their knee pain on the NRS. This initial evaluation is based on the current severity of the pain, regardless of whether patients received any analgesics prior to obtaining radiography. Study will not begin until plain film imaging has been reviewed by a radiologist, at which point patients will be considered for eligibility.

Utilizing a random number generator, patients will be randomized to either the intervention arm (GNB) or the control (conventional analgesia) arm. Within the intervention arm, a three-point GNB will be performed under ultrasound guidance using 80% of ideal body weight (80% of *actual* body weight if BMI is less than 25 kg/m^2) dosing of 0.5% bupivacaine with 4 mg dexamethasone, divided into three separate aliquots (5 mL of 0.5% bupivacaine with 1-2 mg dexamethasone) which will be administered to the SMGN, SLGN, and IMGN. The performing

physician will first identify all landmarks via ultrasound, which include the superomedial and -lateral knee (aligning the probe longitudinally with the femoral condyle) and the inferomedial knee (aligning the probe longitudinally with the tibial condyle). Color doppler will be applied to note any vascular structures within the field of view of injection. The patient will be placed on the cardiopulmonary monitor prior to the GNB. The GNB will be performed via ultrasound guidance in real-time.

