4.3 Justification for Dose

For the GNB arm, the maximum recommended dosing for bupivacaine for regional anesthesia is 2.5 mg/kg. To minimize the risk of LAST, we will utilize weight-based dosing at 80% of the maximal safe dosing which will allow for effective and prolonged analgesia while minimizing the risk of complications and LAST. Patients with body mass index (BMI) greater than 25 kg/m^2 will receive a total of 80% of their ideal body weight dosing in bupivacaine. Patients with a BMI of equal to or less than 25 kg/m^2 will receive a total of 80% of their actual body weight dosing in bupivacaine. This total amount will be divided into three equal aliquots that will be injected around the three genicular nerves), which will be well below the recommended maximal dose for both female and male patients. Dexamethasone dosing ranging from 4-8 mg has shown to prolong regional anesthesia by the prevention of enzymatic processing of local anesthetics, and is commonly used as an adjuvant in both the perioperative setting and in the ED. Given the relatively low volume and dose of anesthetic that will be administered, we plan to supplement the blocks with 4 mg dexamethasone, divided equally into the three injections.

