6.2.2 Formulation, Appearance, Packaging, and Labeling

For the GNB arm, bupivacaine 0.5% is stored in either the Omnicell (immediately available medication storage within the emergency department) or central pharmacy, where it can be sent down to the ED. The medication is stored at room temperature in individually sealed vials. No preparation other than drawing up the medication with a needle and syringe will be necessary, which will be the responsibility of the participating physician administrating the GNB. Vials are single use and clearly labelled. Bupivacaine will be mixed at the bedside with dexamethasone prior to injection. Bupivacaine on formulary is manufactured by Xellia Pharmaceuticals LLC. Dexamethasone 4mg/mL is also available in the ED Omnicell and commonly utilized in emergency patient care. Bupivacaine 0.5% is distributed by Hospira and dexamethasone sodium phosphate 4mg/mL is distributed by Hikma.

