6.2.4 Preparation

For the GNB arm, bupivacaine 0.5% is available in single-use vials as a ready-to-use liquid. It will be drawn up with a blunt needle and syringe and requires no special preparation prior to administration. In this case, three separate syringes will be loaded with the appropriate volume 0.5% bupivacaine (weight-based dosing as described above). To each syringe, 1-2 mg of dexamethasone will be added to the bupivacaine (for a total of 4 mg of dexamethasone).

Preparation of medications for the control arm will be prepared and administered to the patient by nursing as per the electronic orders, as is standard of care.

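### Section 6.1.1 gives the dexamethasone in the block as 4 mL, while the rest of the protocol gives 4 mg in total; at the stocked 4 mg/mL the two differ fourfold

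*Protocol*

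**What the plan says.** Section 6.1.1 (Study Intervention Description) defines the active arm as a one-time three-point block with "weight-based 0.5% bupivacaine and 4 mL dexamethasone divided into three separate injections". The adjuvant is given there as a volume.

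Elsewhere the total is given as a mass:

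- Section 1.1, study description: "weight-based dosing 0.5% bupivacaine augmented with 4 mg dexamethasone, divided into three separate aliquots".
- Section 1.1, description of the intervention: "ideal bodyweight-dosed bupivacaine 0.5% and dexamethasone 4 mg".
- Section 4.1: "dosing of 0.5% bupivacaine with 4 mg dexamethasone, divided into three separate aliquots", with each aliquot described as "5 mL of 0.5% bupivacaine with 1-2 mg dexamethasone".
- Section 4.3: "4 mg dexamethasone, divided equally into the three injections". The same section cites 4-8 mg as the range reported to prolong regional anesthesia.
- Section 6.1.2 (Dosing and Administration): 4 mg over three injections.
- Section 6.2.4 (Preparation), for each syringe: "1-2 mg of dexamethasone will be added to the bupivacaine (for a total of 4 mg of dexamethasone".
- Section 6.5 (Concomitant Therapy): 4 mg in three aliquots.

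On the product, Section 6.2.2 states "Dexamethasone 4mg/mL is also available in the ED Omnicell", and Section 6.2.3 gives the same strength.

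**The concern.** A volume and a mass can be compared only through a concentration. Here the protocol supplies one, and at that concentration the two statements are not the same amount. The conflict sits in the section whose purpose is to describe the intervention, and nothing in that section marks the unit as an error.

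The quantity is acted on directly. Under Section 6.2.1 the participating physician orders both drugs and receives them in unopened vials. Under Section 6.2.2 the two are mixed at the bedside. Enrollment runs across four emergency departments, and Section 4.1 allows the performing physician to be someone other than the treating physician. Two consequences follow from the documents alone:

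- Preparations could differ between operators who each followed a written passage.
- The deviation process in Section 10.1.9 would have no single reference amount against which to judge a preparation.

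**Working it through.** **Inputs**

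- Volume in Section 6.1.1: 4 mL.
- Total mass in Section 1.1 (twice) and Sections 4.1, 4.3, 6.1.2, 6.2.4 and 6.5: 4 mg.
- Stocked strength in Sections 6.2.2 and 6.2.3: 4 mg/mL.
- Amount per syringe or aliquot in Sections 4.1 and 6.2.4: 1-2 mg, for three of them.
- Range cited in Section 4.3: 4-8 mg.

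**Step 1. Can the 4 mg total be built from the preparation instruction?**

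Three syringes at 1-2 mg hold between 3 × 1 = 3 mg and 3 × 2 = 6 mg. The stated 4 mg lies within 3-6 mg, so the total in Section 6.2.4 is attainable as described.

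**Step 2. Does the equal split in Section 4.3 fit the same instruction?**

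4 mg / 3 = 1.33 mg per injection, which lies inside 1-2 mg. Sections 4.1 and 6.2.4 both state the 4 mg total beside the range, so the range cannot be read as permitting a total of 3 mg or 6 mg. The wording in Section 4.3 is tighter than in the other two, but the three are consistent.

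**Step 3. Convert Section 6.1.1 to a mass (mass = volume × concentration).**

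4 mL × 4 mg/mL = 16 mg. Split equally, this is 16 / 3 = 5.33 mg per injection.

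**Step 4. Convert the other sections to a volume (volume = mass / concentration).**

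4 mg / (4 mg/mL) = 1 mL.

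**Step 5. Compare.**

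| | Section 6.1.1 | All other statements of the total |
|---|---|---|
| Volume at 4 mg/mL | 4 mL | 1 mL |
| Mass | 16 mg | 4 mg |
| Mass per injection, equal split | 5.33 mg | 1.33 mg |

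The ratio is 16 / 4 = 4. The 16 mg is above the 3-6 mg that three syringes of 1-2 mg can hold, and it is twice the upper end of the 4-8 mg range (16 / 8 = 2).

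**Step 6. Effect on the injected mixture (illustration only).**

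Take the 5 mL bupivacaine aliquots mentioned in Section 4.1; the dose is otherwise weight-based, so this is an assumption. Three aliquots of 0.5% (5 mg/mL) are 15 mL and 75 mg.

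- With 1 mL added: 75 / 16 = 4.69 mg/mL, about 0.47%.
- With 4 mL added: 75 / 19 = 3.95 mg/mL, about 0.39%.

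The two readings therefore differ in the concentration of the local anesthetic as well as in the amount of dexamethasone.

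**The case against.** The strongest reply is that this is one unit in one descriptive sentence, most likely a slip. The sections an operator would naturally use to dose and prepare the block are 6.1.2 and 6.2.4. Both give milligrams, and they agree with each other and with the remaining statements. Section 6.2.1 also has clinical pharmacists approve the ordered medications before nursing releases them. All of this stands, and it lowers the chance that anyone would prepare the block from Section 6.1.1 alone. It does not remove the contradiction: approval of an order comes before the drug is drawn up and mixed, and a protocol should not state two amounts of an injected drug.

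Three stronger readings are tempting, and the documents do not support them.

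- A reader might infer a second dose conflict from the 1-2 mg per syringe against the equal split. Steps 1 and 2 show that there is none.
- A reader might infer that the duration-of-analgesia endpoint or participant safety is compromised. Sections 4.3 and 6.5 say that dexamethasone is there to prolong the block, and duration is a secondary endpoint. However, the protocol gives no dose-response relation and describes no harm from a larger amount, so any such effect is undemonstrated.
- A reader might treat the 4-8 mg range as a limit that 16 mg breaches. Section 4.3 offers it as background. It shows that the protocol's own justification does not cover 16 mg, and nothing more.

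This is also an inconsistency of units between passages. No calculation printed in the protocol is wrong.

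**Conclusion.** The contradiction is real and lies in the text that describes the intervention. Section 6.1.1 and the seven other statements of the total differ by a factor of four: 16 mg against 4 mg, or 4 mL against 1 mL. The size rests on one assumption, that the product used is the 4 mg/mL one named in Sections 6.2.2 and 6.2.3; the protocol names no other strength.

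The agreement of the dosing and preparation sections makes a wrong preparation less likely, and no consequence for any endpoint is established. The point still has to be settled because it concerns the quantity of an injected drug. The documents cannot be used here to say which amount is right, and this conclusion takes no position on that.

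**What to change.** Reconcile Section 6.1.1 with Sections 1.1, 4.1, 4.3, 6.1.2, 6.2.4 and 6.5, so that the protocol states one total quantity of dexamethasone in one unit throughout, together with the matching volume of the stocked product. The investigators responsible for the intervention must determine the quantity. Using one wording for the split across the three syringes would be tidier, but that is optional.

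The cost is a one-line correction in a protocol amendment and a short note to the performing physicians at the four sites. Sample size, endpoints and analysis are not affected. If any participants have already received the block, check the recorded dexamethasone amounts against the reconciled text.

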2.2.2 Assessment for Potential Study Products Drug-Drug, Drug-Device, Device-Device Interactions

Potential interactions of bupivacaine include:

Local Anesthetics: Toxic effects of local anesthetics are additive, such that administration of multiple anesthetics can increase the risk of systemic toxicity if greater than weight-based dosing limit.

Monoamine Oxidase Inhibitors and Tricyclic Antidepressants: Co-administration of bupivacaine with these agents can produce severe, prolonged hypertension if administered systemically.

Ergot-Type Oxytocic Drugs: Co-administration of bupivacaine with these agents can produce severe, prolonged hypertension or cerebrovascular accidents if administered systemically.

Nonselective Beta-Adrenergic Antagonists: Co-administration of bupivacaine with these agents can cause severe hypotension and bradycardia if administered systemically.

Drugs Associated with Methemoglobinemia: Co-administration of bupivacaine with the following classes of agents can increase risk of developing methemoglobinemia: Nitrates (nitric oxide, nitroglycerin, nitroprusside, nitrous oxide), Antineoplastic agents (cyclophosphamide, flutamide, hydroxyurea, ifosfamide, rasburicase), Antibiotics (dapsone, nitrofurantoin, para-aminosalicylic acid, sulfonamides), Antimalarials (chloroquine, primaquine), Anticonvulsants (phenobarbital, phenytoin, sodium valproate).

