2.2.4 Dosing Rationale

The weight-based maximal safe dosing for bupivacaine is 2.5 mg/kg. To minimize the risk of LAST, we will utilize weight-based dosing at 80% of the maximal safe dosing which will allow for effective and prolonged analgesia while minimizing the risk of complications and LAST. Patients with body mass index (BMI) greater than 25 kg/m² will receive a total of 80% of their ideal body weight dosing in bupivacaine. Patients with a BMI of equal to or less than 25 kg/m² will receive a total of 80% of their actual body weight dosing in bupivacaine. This total dose will

be divided into three equal aliquots that will be injected around each of the three targeted genicular nerves. The use of dilute bupivacaine (0.5%) will allow for better spread to target nerves as well as a slower injection rate of anesthetic which is safer for monitoring for symptoms of LAST.

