The control arm will be treated with oral, intravenous, or topical analgesics, as per the treating clinician's discretion. Patients will be observed on continuous cardiorespiratory monitoring in the ED for at least 30-minutes following treatment to evaluate for treatment effect and adverse events. Patients will be discharged from the ED when their pain is sufficiently controlled, and they are agreeable for discharge. Of note, patients in both treatment arms will be eligible for additional analgesics, as needed, at any point after enrollment. This will be recorded and evaluated during analysis. At either 1-hour after enrollment or at the time of discharge from the ED (whichever occurs first), patients of both treatment arms will be again asked to rate their pain severity on the NRS and asked to complete the modified APS-POQ-RED. This survey will be conducted either by RAs (during daytime hours, if available) or the performing physician (if overnight). Patients will subsequently receive a phone call approximately 24 to 36 hours after the treatment by a member of the study team (performing physician, RA, or the clinical research coordinator (CRC) from the Emergency Ultrasound Division) to evaluate the duration of analgesia. If the block is performed during overnight hours, the follow-up call will take place the next day (between 24 to 36 hours after treatment). After this assessment, the participant's involvement in the study will be concluded. Only in cases where an adverse event occurred that either requires hospitalization or ambulatory follow-up will a participant's participation last longer than 24 hours. All data collected by the RA, the CRC, or the performing physician will be stored in REDCap. The RAs will transmit all research data, including an encrypted medical record number (MRN) and all pain scale responses obtained from the study participants to the Ultrasound Division's CRC, who will be responsible for storing and managing data on REDCap.

Patients with large knee effusions will not be included in the study as large effusions can make the GNB more difficult to perform by distorting the anatomical and sonographic landmarks, and we wish to avoid the additional risk of inadvertent intra-articular injections. In our experience, we have been able to perform the GNB on patients with small and moderate sized effusions without difficulty.

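### Section 6.1.2 states the bupivacaine limit per kg of ideal weight but doses patients with BMI below 25 on actual weight, so the claimed margin is not guaranteed on that scale

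*Protocol*

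**What the plan says.** Three statements in protocol section 6.1.2 bear on the margin:

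- The limit and the promise: dosing is set so that "the total amount of bupivacaine will fall well under the maximum recommended dosing by weight (2.5 mg/kg ideal body weight").
- The dosing rule, in the sentence that follows: "80% of ideal body weight-based (actual body weight for patients with BMI less than 25" kg/m²).
- The precaution for older patients, further down the same section: "To minimize these risks, we are utilizing 80% of their ideal body weight dosing of bupivacaine". No exception for lower BMI is repeated there.

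Elsewhere the limit carries no weight scale. Section 2.2.4 says that "The weight-based maximal safe dosing for bupivacaine is 2.5 mg/kg" and that "we will utilize weight-based dosing at 80% of the maximal safe dosing". Section 4.3 says that "the maximum recommended dosing for bupivacaine for regional anesthesia is 2.5 mg/kg". Both sections use actual weight at a BMI of 25 or less. Section 2.3.1 uses ideal weight from BMI 25 upward and actual weight below it, and lists this first among its measures against local anaesthetic systemic toxicity (LAST). Sections 2.3.3 and 4.1 also switch to actual weight below BMI 25. Section 4.1 in addition describes each aliquot as 5 mL of 0.5% bupivacaine, which is a fixed volume. No section gives a formula for ideal weight.

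**The concern.** A dose set on one weight and a limit set on another do not stand in a fixed ratio. Section 6.1.2 promises a comfortable distance from a limit per kg of ideal weight. For patients with BMI below 25, however, that distance depends on how far actual weight lies from ideal weight, and the protocol does not define ideal weight.

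The sentence on older patients raises the same problem without any formula. It answers the regulator's caution on geriatric use partly by pointing to ideal-weight dosing, but an older patient with BMI below 25 is dosed on actual weight.

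At stake is whether a safety statement on which the ethics board and the operators rely is true for every eligible patient. No endpoint, sample size or power figure depends on it.

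**Working it through.** **Inputs from the protocol.** Limit 2.5 mg/kg (2.2.4, 4.3; per kg of ideal weight in 6.1.2). Fraction given 80% (2.2.4). Actual weight is the dosing weight below BMI 25 (6.1.2). Fixed aliquot 5 mL of 0.5% solution, three injections (4.1).

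**Step 1: the plan's own figure.** Dose = 0.80 × 2.5 = 2.0 mg per kg of dosing weight. When dose and limit use the same weight, 2.0 / 2.5 = 80%. The stated figure reproduces.

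**Step 2: BMI below 25, on the scale of 6.1.2.** With actual weight A and ideal weight I, the dose is 2.0 × A and the limit is 2.5 × I.

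Share of limit = (2.0 × A) / (2.5 × I) = 0.80 × A/I

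The share is 80% only if A = I, is higher whenever A > I, and is 100% at A/I = 1/0.80 = 1.25. This step needs no outside figure.

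**Step 3: size. Assumption: the protocol gives no ideal-weight definition, so a range is shown, all at BMI 24.9.**

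(a) Ideal weight as the weight at a reference BMI. Then A/I = 24.9 / reference BMI, at any height.

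| Reference BMI | 19 | 20 | 21 | 22 | 23 | 24 |
|---|---|---|---|---|---|---|
| Share of limit | 105% | 99.6% | 95% | 91% | 87% | 83% |

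The limit is reached only if the reference BMI is 24.9 / 1.25 = 19.9 or lower.

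(b) A linear height formula: 45.5 kg (women) or 50 kg (men) plus 2.3 kg per inch over 60 inches. For a woman of 152.4 cm (60 inches), A = 24.9 × 1.524² = 57.8 kg. The dose is 115.7 mg against a limit of 2.5 × 45.5 = 113.8 mg, a share of 102%.

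| Height | Women | Men |
|---|---|---|
| 150 cm | 103% | 94% |
| 152.4 cm | 102% | 92.5% |
| 155 cm | 100% | 91% |
| 160 cm | 97% | 90% |
| 170 cm | 94% | 87% |
| 190 cm | 90% | 86% |

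The 150 cm row extends the formula below 60 inches. Under this formula the limit is reached in women up to 155.0 cm at BMI 24.9, up to 152.4 cm at BMI 24.5 and up to 149.6 cm at BMI 24.

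(c) Four linear formulas of this kind were tried over 145 to 190 cm. Two pass the limit in women up to about 155 cm, and one of these also does so in men of about 145 cm. The other two stay between 80% and 98%. The highest value is 108%, at 145 cm, again by extension below 60 inches.

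**Step 4: the fixed aliquots of 4.1.** 0.5% is 5 mg/mL, so the total is 3 × 5 mL × 5 mg/mL = 75 mg. That is below 2.5 mg/kg for any ideal weight above 75 / 2.5 = 30 kg. It is also not a weight-based dose: the woman of 152.4 cm in (b) would get 115.7 mg under the weight-based rule.

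**The case against.** The strongest defence is that the mismatch rests on a single parenthesis. Sections 2.2.4 and 4.3 give the limit without a weight scale, and section 2.3.1 can be read as pairing dose and limit on the same weight in each BMI group. On that reading every patient gets exactly 80%. This stands, and it rules out saying that the 80% is miscalculated. It does not rescue 6.1.2, the operative dosing section, which names ideal weight for the limit and then doses some patients on another weight.

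A reader might infer that the rule takes patients past the maximum dose. The documents do not support that as a general statement. It needs an ideal-weight formula that they do not give, it fails under several plausible ones, and where it holds it concerns mainly short women close to BMI 25. It also disappears if the 75 mg total of section 4.1 is followed. That volume contradicts the weight-based rule, though, so it adds to what must be reconciled and does not settle it.

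On older patients, the exception for BMI below 25 does appear earlier in the same section, and the passage also relies on at least 30 minutes of monitoring and available reversal therapy. The margin is therefore not the only precaution. The sentence still describes a dosing basis that does not apply to older patients with BMI below 25.

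A reader might also infer that lidocaine patches use up the margin. Section 2.2.2 says "Toxic effects of local anesthetics are additive", with the weight-based limit as the reference. The patches are listed among conventional analgesics, and section 4.1 says "patients in both treatment arms will be eligible for additional analgesics, as needed, at any point after enrollment". No section says whether they count toward the limit. However, the documents give nothing from which the effect could be sized, and the silence contradicts no stated figure. It is a secondary note only.

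**Conclusion.** The concern holds in a limited form. On the scale that section 6.1.2 itself names, the margin for patients with BMI below 25 is not a guaranteed 80% of the limit but 0.80 × actual/ideal weight. That follows from the protocol alone. The statement on older patients is not the rule for those with BMI below 25, and that too needs no outside figure.

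The size depends on an assumed ideal-weight definition. At BMI 24.9 the share is roughly 80% to 105%. The limit is reached only under some formulas, mainly in women of about 155 cm or less, or if ideal weight corresponds to a BMI of about 20 or less. If limit and dose are meant on the same scale, the margin is exactly 80% and the fault is one of wording. How many patients are affected cannot be estimated, because the protocol gives no distribution of height or BMI.

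**What to change.** Reconcile sections 2.2.4, 2.3.1, 2.3.3, 4.1, 4.3 and 6.1.2, including its paragraph on older patients, so that the stated limit and the dosing weight use the same scale, and name the ideal-weight formula. The alternative is to leave the rule as it is, state the true margin for patients with BMI below 25, and correct the sentence on older patients. Either way, the fixed aliquot volume in 4.1 has to be squared with the weight-based dose. As a secondary matter, the sponsor could say whether other local anaesthetics given before or after the block count toward the limit; section 6.4 already has these drugs recorded.

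Which scale, formula or volume is right is for the sponsor's clinicians. The cost is a wording amendment with no effect on sample size or analysis. The stated margin may come out less favourable for some patients than the protocol now says.
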